### 3.3 Long Term Endpoints

The primary long-term efficacy endpoint regarding the cell product and its delivery procedure is:

Change in right ventricular cardiac function at 12 months post-Stage II surgery compared to baseline, measured by echocardiogram.

Secondary long-term efficacy safety endpoints in their order of relevance and importance in this clinical study are:

- 1) Change in weight every 6 months post-Stage II surgery compared to baseline.
- 2) Change in heart failure medication taken every 6 months post-Stage II surgery compared to baseline.
- 3) Change in arrhythmia medication taken every 6 months post-Stage II surgery compared to baseline.

- 4) Success of subject being scheduled for Stage III surgical repair.
- 5) Time (days) until listed for cardiac transplantation, or death following the 6-month follow-up.
- 6) Change in right ventricular function at Stage III surgery pre-op work-up compared to baseline, obtained by echocardiogram, cardiac MRI, and cardiac catheterization.

Additional variables may be assessed in an exploratory manner.

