In the context of the feasibility of UCB collection and manufacturing, the study protocol and manufacturing SOPs ensure a high yield of available products to clinical sites for investigational cell therapy under this IND in subjects that participated in the UCB Collection Study. From the 98 consented patients that intended to undergo umbilical cord blood collection as participants in the Mayo Clinic UCB Collection Study, 80 patients had umbilical cord blood collected and received by the manufacturer. The 18% failure to collect/manufacture a UCB-derived product was most commonly related to mothers delivering early or mothers consenting too late, which affected the feasibility of the logistics. The majority of UCB collection failures have not been related to technical problems in the past 12 months as these have been effectively addressed with improvements in training of staff involved in UCB collections and manufacturing SOP refinements. The UCB collection failure rate will be further reduced with dedicated UCB training within the Phase IIb clinical sites. During the Phase I Study, on December 1, 2016, the product manufacturing was transitioned to a partnering CMO, ReGen Theranostics (Rochester, MN). Manufacturing of the last 40 products as of March 2018 at ReGen have resulted in 37 products available for release (92% success rate). The three products that were not made available for release were due to 1) a manufacturing error that was an unacceptable quality control issue, 2) a critical labeling issue between collection and manufacturing that was not able to be reasonably resolved, and 3) a low cell recovery linked to a low collection volume that

limited the manufacturing yield of that product. The manufacturing and UCB collection logistics have been refined such that they will be unlikely to limit enrollment and treatment in the Phase IIb study.

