## 3 STUDY DESIGN

### 3.1 General Design

This Phase IIb study is a multicenter, prospective, open-label, non-randomized, observational study designed to evaluate the efficacy and safety of UCB-MNC delivered into the right ventricular myocardium of subjects with HLHS or HLHS variants with right ventricular dependent single ventricular CHD at the time of a planned Stage II surgical repair. This will be achieved by comparing the data collected in the treatment group (Arm A) to the equivalent data collected in the control group (Arm B), adjusting for baseline.

The concurrent control arm (Arm B) must meet identical study eligibility criteria as the treatment arm (Arm A), except for the requirements related to UCB-MNC product acceptability and DMSO sensitivity. The control arm will undergo the same planned Stage II surgical repair without the investigational cell delivery add-on procedure and will follow-up post-surgery in the same manner as the treatment arm (see Section 6 of this protocol).

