#### 3.1.1 Treatment Assignment

[figure not shown]
When possible, prior to enrollment in this study, expecting parent(s) with prenatal diagnosis of HLHS or HLHS variants will be offered enrollment in a separate, ongoing Umbilical Cord Blood Collection Study for the collection of UCB. The parent(s) and/or legal guardian(s) may be consented to allow their child to participate in the treatment group (Arm A) of this clinical study if the patient requires Stage II surgical repair, if the autologous UCB-MNC manufactured product is determined to be acceptable for release to the investigational site for clinical use, and if the subject meets all other eligibility criteria for this study. Patients without frozen UCB-MNC product or without UCB-MNC product determined to be acceptable for clinical use in this study may be consented to the control arm of this clinical study if the subject meets all non-treatment-only eligibility criteria for this study.

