### 3.2 Short Term Endpoints

The primary short-term efficacy endpoint regarding the cell product and its delivery procedure is:

Change in right ventricular cardiac function at 3 months post-Stage II surgery compared to baseline, measured by *apical fractional area change, circumferential strain, and longitudinal strain on echocardiogram*.

Secondary short-term efficacy and safety endpoints in order of their relevance and importance in this clinical study are:

- 1) Change in cardiac function between baseline and hospital discharge for Stage II surgery, measured by echocardiogram.
- 2) Cumulative days of hospitalization per patient at 1 and 3-months post Stage II surgery.
- 3) Change in weight, heart rate, and oxygen saturation at 3-months post Stage II surgery compared to baseline.

Additional variables may be assessed in an exploratory manner.

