## 4 SUBJECT ELIGIBILITY ASSESSMENTS, ENROLLMENT, AND WITHDRAWING SUBJECTS

### 4.1 Eligibility for This Study:

Both sexes with HLHS or HLHS variants with right ventricular dependent single ventricular CHD requiring planned Stage II surgical repair that meet the following inclusion and exclusion criteria are eligible to participate in this study. Inclusion and exclusion requirements may be specific to the treatment arm only and will be specified as such in parentheses.

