#### 4.1.1 Inclusion Criteria

1. Diagnosis of HLHS or HLHS variant with single right ventricular dependent CHD having undergone Stage I surgical repair and undergoing Stage II surgical repair.
2. Less than 13 months of age at time of Stage II surgical repair.
3. Previous participation in the UCB collection protocol with autologous UCB-MNC product that is acceptable for use (treatment arm only).

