#### Secondary Outcomes

Quantitative long-term outcomes will be analyzed like the primary long-term efficacy outcome of apical fractional area change. Yes/no outcome variables like “able to undergo Stage III palliative surgery” will first be analyzed by describing percent by group and the groups

compared using a chi-square test. We will analyze time-to-event outcomes, like time to listing for cardiac transplant or death, first describing naïve rates with the Kaplan-Meier method and then using Cox regression models including terms for treatment group and baseline cardiac function. If the primary analysis suggests dependency of treatment on cardiac function, we will also repeat these analyses considering cardiac function as an effect modifier by including interaction terms between group and baseline cardiac function.

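### Weight change is adjusted for baseline weight but not for age or sex, so an age difference between the non-randomised arms can partly appear as a treatment effect

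*Combined protocol and SAP*

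**What the plan says.** Weight is an efficacy outcome in two places. Short-term secondary 3 (section 3.2) is "Change in weight, heart rate, and oxygen saturation at 3-months post Stage II surgery compared to baseline". Long-term secondary 1 (section 3.3) is "Change in weight every 6 months post-Stage II surgery compared to baseline". Neither names a growth standard or a z-score.

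Section 7.4.3 handles the short-term secondaries like the primary outcome. For the long term, section 7.4.4 says: "Quantitative long-term outcomes will be analyzed like the primary long-term efficacy outcome of apical fractional area change". The primary model has a treatment term and the baseline value of the outcome. The Clinical Study Summary defines that value as the same variable measured at Stage II surgery, which for weight is baseline weight.

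The population is "Both sexes with HLHS or HLHS variants with right ventricular dependent single ventricular CHD" (section 4.1), and the only age limit is "Less than 13 months of age at time of Stage II surgical repair" (section 4.1.1). The design is a "multicenter, prospective, open-label, non-randomized, observational study" (section 3.1). On entry to Arm B, section 3.1.1 says in part: "Patients without frozen UCB-MNC product or without UCB-MNC product determined to be acceptable for clinical use in this study may be consented to the control". Section 1.4 reports that failure to obtain a product in the earlier collection study "was most commonly related to mothers delivering early or mothers consenting too late".

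**The concern.** Two infants of equal weight but different age have different expected gains: one may be small for an older age, the other average for a younger one. Baseline weight is therefore an imperfect stand-in for age, and adjusting for it leaves part of any age difference in the treatment estimate.

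Randomisation would make such a difference a matter of chance. Here the arm depends on whether a usable product exists and whether the family accepts treatment. Early delivery and late consent are documented reasons for having no product. The arms could therefore differ in gestational maturity, and possibly in age at surgery. At stake is the reading of growth, which section 2 lists among the objectives, at 3 months and every 6 months thereafter. The primary cardiac-function endpoint is not affected by this point.

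**Working it through.** **Inputs from the documents.** Age under 13 months (4.1.1); non-randomised arms (3.1); baseline value of the same variable as the only covariate (Clinical Study Summary, 7.4.3); alpha 0.05, 50 per arm, or 30 per arm after 40% loss (7.1). The documents give no age distribution, growth curve or SD for weight.

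**The plan's own figures.** Section 7.1 gives detectable effects of 0.57 and 0.74, for cardiac function. The normal approximation gives (1.960 + 0.842)/√(50/2) = 0.560 and 2.802/√(30/2) = 0.723. A two-sided t test gives 0.566 and 0.736, so the figures reproduce. No power is stated for weight.

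**Assumptions (not in the documents).** Age at surgery has mean 5 and SD 1.5 months, and the treatment arm is older by 0 to 2 months. Weight velocity at age a is 0.17 + 0.38 × 0.85^(a−4) kg/month, that is 0.55 at 4 months and 0.49 at 5. Baseline weight is 3.2 kg plus 0.75 times the curve's gain since birth, plus 0.3 kg for one sex, with between-child SD 0.5–0.8 kg. Six-month gain follows the curve, plus 0.1 kg for that sex, with residual SD 0.5 kg.

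**Step 1: unadjusted difference.** Six-month gain from age a is 0.17 × 6 + 0.38 × 0.85^(a−4) × (1 − 0.85^6)/(−ln 0.85). Since (1 − 0.377)/0.1625 = 3.83, this gives 2.48 kg at 4 months, 2.26 at 5, 2.07 at 6 and 1.91 at 7. Around age 5, an arm older by 1 month gains 2.26 − 2.07 = 0.19 kg less. An arm older by 2 months gains 2.26 − 1.91 = 0.35 kg less.

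**Step 2: what baseline weight removes.** Roughly, it removes the share of within-arm weight variance that is due to age. Weight rises by about 0.75 × 0.49 = 0.37 kg per month of age, so age contributes (0.37 × 1.5)² = 0.31. Sex contributes 0.3² × 0.25 = 0.02, and between-child variation 0.5² = 0.25 to 0.8² = 0.64. The share is 0.31/0.58 = 0.53 down to 0.31/0.97 = 0.32. About 47–68% of the bias stays.

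**Step 3: simulation.** True effect zero, 50 per arm, 2,000 runs per cell; ranges cover the two between-child SDs. Entries are bias in kg and false-positive rate.

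| Treatment arm older by | Unadjusted change | Planned model | Planned model + age, age², sex |
|---|---|---|---|
| 0 months | 0.00 to 0.01; 5% | 0.00; 5–6% | 0.00; 5% |
| 0.5 month | −0.09; 12–13% | −0.05 to −0.07; 7–10% | 0.00; 5–6% |
| 1 month | −0.18; 34–37% | −0.10 to −0.13; 13–19% | 0.00; 4–5% |
| 2 months | −0.34; 84% | −0.19 to −0.26; 35–59% | 0.00 to 0.01; 5% |

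The planned model keeps 50–75% of the unadjusted bias (for example 0.257/0.342 = 0.75), in line with step 2. With 30 per arm its false-positive rate is 10–14% at 1 month and 22–38% at 2 months. The sign reverses if the treatment arm is the younger one.

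**Step 4: other assumptions, 50 per arm.**
- Same velocity curve, residual SD 0.8–1.0 kg, no sex effect, and baseline weight following the full curve (no 0.75 factor). The planned model has bias 0.06–0.11 kg and 5–10% false positives at 1 month, and 0.12–0.20 kg and 8–21% at 2 months.
- Velocity falling in a straight line from 4 to 10 months (0.50 to 0.30, 0.60 to 0.25, or 0.45 to 0.35 kg/month) and flat thereafter, residual SD 0.8 kg. About one-third to three-fifths of the bias remains, with 6–13% false positives at 1 month and 5–35% at 2 months.

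Across steps 3 and 4 the planned model's rate is about 5–19% for 1 month and 5–59% for 2 months. Adding age restored about 5% each time. The 3-month outcome was not simulated.

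**The case against.** The best defence is that the plan does not compare raw gains. Baseline weight is in the model and, in the main simulation, removes 25–50% of the age bias. The higher false-positive rates need a residual SD as low as 0.5 kg; with 0.8–1.0 kg they fall sharply. Section 7.3 describes baseline demographics by arm, so an imbalance would be visible. All of this stands and limits the size. It does not close the gap, because seeing an imbalance is not adjusting for it. The Clinical Study Summary lets other, unnamed baseline values enter only through secondary effect-modification models, and section 7.4.6 adds hospital, not age or sex.

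Four stronger readings are tempting and are not supported:
- A reader might infer that the arms do differ in age. No document gives an age difference. Section 1.4 offers a mechanism, and a more direct one for gestational age than for age at surgery.
- A reader might take the unadjusted difference for a 2-month gap, 0.20–0.69 kg under straight-line curves, divide it by an SD of 0.8–1.0 kg, and set the resulting 0.2–0.9 SD against 0.57. The planned model is not unadjusted, and 0.57 belongs to cardiac function.
- A reader might think a linear age term is inadequate. If velocity is linear in age, gain over a fixed interval is exactly linear in starting age: (0.50 − 0.30)/6 × 6 = 0.20 kg per month of age. Under the curved velocity, a linear term left at most 0.02 kg of bias and 4–7% false positives.
- A reader might infer that weight strictly gates the later long-term endpoints. The Multiplicity paragraph of section 7.3 sets an order for assessing significance but states no rule for stopping after a non-significant result.

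**Conclusion.** The point holds in conditional form. As written, the weight analysis has no protection against an age difference between arms beyond what baseline weight provides. For a 2-month difference in mean age, the bias left at 6 months is about 0.12–0.26 kg under the curved growth assumption. The width of the false-positive ranges reflects how little is known about the growth curve, the between-child SD and the residual SD of gain (0.5–1.0 kg) in this population. The problem is negligible if the arms are balanced in age, or if growth follows the flattest curve considered. Sex matters only if its mix differs by arm. The direction cannot be predicted from the documents: a younger treatment arm would flatter the product, and an older one would count against it. The outcome is secondary, so this should be corrected in the plan but does not undermine the trial's main comparison.

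**What to change.** Either of two changes would serve:
- In sections 7.4.3 and 7.4.4, add age at surgery and sex to the covariance model for weight.
- In sections 3.2 and 3.3, define growth as change in weight-for-age z-score, sex-specific and using exact age at each measurement, with covariance adjustment for baseline z-score. Kilograms stay as a descriptive display.

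With either, report age at surgery by arm. If gestational age is captured, correct the z-score for it or add it as a covariate, because early delivery is a documented reason for lacking product. The baseline list in section 6.1.1 does not name gestational age, so its availability should be confirmed.

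The cost is a few lines of text. Weight is already collected (6.1.1, 6.3.2, 6.3.3), age is needed for eligibility, and demographics are already to be described by arm (7.3). No visit, procedure or sample-size change follows.

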**CLINICAL STUDY SUMMARY**

Title	Phase IIb Study of Intramyocardial Injection of Autologous Umbilical Cord Blood Derived Mononuclear Cells during Stage II Surgical Repair of Hypoplastic Left Heart Syndrome (AutoCell-II)
Running Title	Phase IIb Efficacy Study of UCB-MNC Intramyocardial Injection for HLHS and HLHS Variants
Protocol Number	CSP-4401
Phase	Phase IIb
Study Design	Prospective, Open label, Non-randomized, Observational Study
Overall Study Duration	6 years
Subject Participation Duration	Up to 4 years or until pre-operative work-up for Stage III surgical palliation has been completed or until cardiac transplant, whichever is first
Single or Multi-Site	Multi-Site
Objectives	This study will evaluate the efficacy and safety of UCB-MNC intramyocardial injections performed during Stage II surgical palliation by focusing on short and long-term cardiac function leading up to the pre-operative work-up for Stage III surgical palliation.
Study Purpose	Determine if the delivery of the autologous UCB-MNC product into the myocardium of the right ventricle of the heart at the time of Stage II surgical repair will provide a short-term improvement in cardiac function, while also providing a reduction in the cumulative days of hospitalization following Stage II surgical repair. Additionally, long-term improvement in cardiac function, growth, reaching Stage III surgical repair pre-op work-up and prolonging time to cardiac transplantation or death will be determined. Reaching developmental milestones and quality of life will also be monitored.
Number of Subjects	30-50 treated subjects receiving cell product, along with 30-50 subjects with standard surgical treatment (not receiving cell product).
Study Population	Subjects less than 13 months of age with HLHS or HLHS variant who are undergoing Stage II surgical palliation.
Study Product, Dose, Route, Regimen	The investigational product is autologous MNC derived from UCB at a concentration of 10-30 million TNC per mL. The investigational product will be delivered into the right myocardium via sub-epicardial injections of 0.1 mL per kg body weight to achieve the target dose of 1-3 million TNC per kg body weight.
Time and Duration of Administration	A single treatment will be administered intraoperatively upon the successful completion of the planned Stage II surgical repair.

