Primary and Secondary Long-Term Endpoints	
The primary long-term efficacy endpoint regarding the cell product and its delivery procedure is:
 
Change in right ventricular cardiac function at 12 months post-Stage II surgery compared to baseline, measured by echocardiogram.
 
Secondary long-term safety and efficacy endpoints in their order of relevance and importance in this clinical study are:
 
 
1) Change in weight every 6 months post-Stage II surgery compared to baseline.
 
2) Change in heart failure medication taken every 6 months post-Stage II surgery compared to baseline.
 
3) Change in arrhythmia medication taken every 6 months post-Stage II surgery compared to baseline.
 
4) Success of subject being scheduled for Stage III surgical repair.
 
5) Time (days) until listed for cardiac transplantation, or death following the 6-month follow-up.
 
6) Change in right ventricular function at Stage III surgery pre-op work-up compared to baseline, obtained by echocardiogram and cardiac catheterization.
 

Statistical Methodology	
Quantitative outcomes, like FAC, at specified time post-surgery, will be analyzed using analysis of covariance to estimate the difference in means between the cell-based therapy and control groups after adjusting for the baseline value (the measured value of the same variable, e.g. FAC, at the time of Stage II surgery). Categorical outcomes, like able to undergo Stage III palliation surgery, will be compared between groups using a chi-square test. Time-to event outcomes, like time until listing for cardiac transplant, will be compared using the Kaplan-Meier method and log-rank test. We will similarly do analyses of other variables based upon this patient subset. In secondary analyses we will also fit models which allow the treatment effect (mean difference between the cell-therapy group control groups) to depend on baseline cardiac function measures or other baseline values. This will be done by using the linear, logistic and Cox regression models as appropriate.

Imaging Core Lab	
M. [name] (Core Lab Director) Mayo Clinic Pediatric and Adolescent Medicine [name] [name]

Contract Manufacturing Organization	
ReGen Theranostics, Inc. [name] [name]

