## 2 STUDY OBJECTIVES

The purpose of this Phase IIb clinical study is to evaluate the efficacy and safety of autologous UCB-MNC intramyocardial injections into the single, morphological right ventricle of subjects with HLHS or HLHS variants requiring Stage II surgical repair. Thirty to fifty treated subjects and thirty to fifty control subjects will be accrued. Subjects accrued in the treatment arm (Arm A) of this study will be treated with a single dose following successful completion of Stage II surgical repair. Subjects accrued in the control arm (Arm B) of this study will be followed according to the same protocol requirements as the treatment arm but will not receive cell therapy. In the treatment and control arms, surrogate markers of cardiac function, growth, success in reaching Stage III surgical repair pre-operative work-up, time to cardiac transplantation or death, and cumulative days of hospitalization will be recorded and evaluated following the completion of Stage II surgery for up to four years, or until the pre-operative work-up for the Stage III surgical repair has been completed or until cardiac transplant, whichever is first. Development and quality of life as measured by questionnaires will also be monitored. Follow-up surrogate markers and the other variables noted above that are recorded for this study will be compared to baseline and by study arm. The surrogate markers and other variables are described in Section 3 of this protocol.

The objective is to evaluate the short-term (up through 3 months post-Stage II surgical repair) cardiac function, growth, and cumulative days of hospitalization following discharge for the Stage II surgical repair in the treatment and control arms, adjusting for baseline.

This evaluation will also include long-term (6 months and up to 4 years post-Stage II surgical repair or until the pre-operative work-up for the Stage III surgical repair has been completed or until cardiac transplant), cardiac function, growth, ability to reach Stage III surgical repair pre-operative work-up and time to cardiac transplantation or death in the treatment and control arms, adjusting for baseline.

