#### 3.1.2 Subject Evaluation

Once consent has been obtained, subjects will enter the screening phase where a pre-operative baseline work-up will be performed as outlined in Section 6 of this protocol. Following the pre-operative work-up, Stage II surgical repair, and final eligibility confirmation according to the inclusion and exclusion criteria listed in Section 4 of this protocol, the subject will be enrolled on to the trial. Following Stage II surgical repair hospitalization, subjects will enter active follow-up. This includes evaluation in-clinic at 3 and 12-months post-Stage II surgical repair, which will include the collection of imaging data. Phone follow-ups will be conducted at 1 month and 6 months post-Stage II surgery and conducted every 6 months following the 12-month in-clinic visit up to pre-operative work-up for the Stage III Fontan palliative surgery, cardiac transplant or to 4 years post-Stage II surgery, whichever is first.

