#### **6.3.4 Pre-Op Stage III Workup Visit:**

- Changes in Concomitant Medications
- AE Assessment
- Physical Exam (including weight)
- Vital Signs (heart rate, blood pressure, oxygen saturation)
- 12 Lead ECG
- Echo (TTE)
- Cardiac Cath (when clinically available)

When the Stage III surgery is scheduled, the date of the Stage III pre-operative work-up and the following standard of care work-up data will be collected from the subject's medical records. If data is not available, the lack of this data will not be considered a protocol deviation. The goal of collecting this data for this study is to evaluate cardiac function that is normally obtained through

standard of care pre-operative testing for the Stage III surgery, without requiring any additional research-only tests/procedures at this time point.

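### Stage III success is scored at scheduling and follow-up ends at the work-up, so a child whose surgery is then cancelled stays a success and exits before later transplant listing or death can count

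*Combined protocol and SAP*

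**What the plan says.** Three wordings describe what appears to be one outcome.

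- **Scheduled.** Section 3.3 (and the Clinical Study Summary) lists long-term secondary 4 as "Success of subject being scheduled for Stage III surgical repair".
- **Reaching the work-up.** Section 2 evaluates "ability to reach Stage III surgical repair pre-operative work-up". The Summary's study purpose and the Section 1 hypothesis say much the same.
- **Able to have the operation.** The Summary's methods state: "Categorical outcomes, like able to undergo Stage III palliation surgery, will be compared between groups using a chi-square test". Section 7.4.4 gives "able to undergo Stage III palliative surgery" as its example of a yes/no outcome.

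Section 7 opens by pointing to Sections 3.2 and 3.3 for the full description of the endpoints.

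On timing and exit:

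- Section 6.3.4 begins its data collection with "When the Stage III surgery is scheduled, the date of the Stage III pre-operative work-up". It then takes medications, adverse events, examination, vital signs, ECG, echocardiogram and, where available, catheterization from the medical record. It also says: "If data is not available, the lack of this data will not be considered a protocol deviation".
- The Summary gives participation as "Up to 4 years or until pre-operative work-up for Stage III surgical palliation has been completed or until cardiac transplant, whichever is first".
- Section 3.1.2 runs the six-monthly phone contacts "up to pre-operative work-up for the Stage III Fontan palliative surgery, cardiac transplant or to 4 years post-Stage II surgery, whichever is first".

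Long-term secondary 5 is the time to transplant listing or death after the 6-month follow-up.

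**The concern.** Being scheduled, completing the work-up and having the operation are different events, and they separate in the children who matter most here: those whose right ventricle is judged inadequate at the work-up. Under the Section 3.3 wording such a child has already been scored a success, and no rule reverses the score if the operation is cancelled or deferred.

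The exit rule adds a second problem. Completing the work-up ends participation whether or not surgery follows. A child turned down at that point plausibly has a raised risk of transplant listing or death, yet is no longer followed for either. Secondary 5 would then be incomplete in a way that depends on prognosis.

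The definition also matters for testing. Section 7.3 (Multiplicity) assesses significance in the listed order and relies on that order to avoid adjustment. Endpoint 4 stands ahead of endpoints 5 and 6, so its meaning should be fixed before data are seen, particularly in an open-label, non-randomized study.

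**Working it through.** **1. The plan's own figures.** Section 7.1 gives no figure for the Stage III endpoint. Its figures concern cardiac function. A two-sample t-test (two-sided alpha 0.05, 80% power) gives a detectable effect of 0.566 SD at 50 per arm and 0.736 SD at 50 × (1 − 0.40) = 30 per arm. These round to the stated 0.57 and 0.74. Nothing below changes them.

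**2. Tracing one child through the text.**

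| Step | Source | Consequence |
|---|---|---|
| Stage III is scheduled | 3.3, secondary 4 | Scored a success |
| Work-up data taken from the chart | 6.3.4 | No clearance or surgery-performed item listed |
| Work-up completed | Summary, 3.1.2, 6.3.3 | Participation ends |
| Surgery cancelled | No rule found | Success stands |
| Later listing or death | After exit | Not counted in secondary 5 |

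Section 7.3 (Lost to follow up) does not repair the last row. It censors children still in the study at analysis and those lost to follow-up, and its investigator override applies only to the latter. Section 4.6 seeks survival status from public records for withdrawn children, but states nothing similar for a child who exits at the work-up.

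**3. How many children.** The documents give no turn-down rate, so every input here is an assumption: 40 of 50 per arm reach the work-up, and a fraction q are not cleared.

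- Expected number per arm = 40q
- Chance of at least one per arm = 1 − (1 − q)^40

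| q | Children per arm | Chance of at least one |
|---|---|---|
| 2% | 0.8 | 55% |
| 5% | 2 | 87% |
| 10% | 4 | 99% |

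**4. What this could do to the comparison.** If a fraction f of the children not able to have surgery is scored as success in each arm, the difference between arms shrinks by the factor (1 − f). Assume true rates of 70% and 90%, a gap of 20 points, with 50 per arm:

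- f = 10%: 50 × 0.30 × 0.10 = 1.5 and 50 × 0.10 × 0.10 = 0.5 children misclassified. The gap becomes 18 points, and chi-square power falls from 71% to 65%.
- f = 25%: 3.75 and 1.25 children misclassified. The gap becomes 15 points, and power falls to 56%.

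The 20-point gap is chosen for illustration and is not a design assumption of the trial.

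**5. A limit on that argument.** Suppose the arms differ only in turn-down, 10% against 2% of 40. With perfect recording, success is 40 − 4 = 36 of 50 (72%) against 40 − 0.8 = 39.2 of 50 (78.4%). Chi-square power is about 11% at 50 per arm and 9% at 30 per arm. A corrected endpoint would rarely detect a difference of that size either.

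**The case against.** Several stronger readings are tempting, and the documents do not support them.

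- **The analysed outcome has no data.** Section 7 hands the definition to Section 3.3, and scheduling is observable. Ability to undergo surgery appears only as an example, introduced by the word like, and may be loose wording. What stands is that the wordings conflict and that the outcome as phrased in 7.4.4 cannot be derived from the listed items.
- **Surgery is never recorded.** The case report forms are not in the documents. The supportable statement is that Section 6.3.4 does not list it.
- **The plan itself says unfit children are successes.** Section 6.3.4 says when chart data are collected, not when clinicians judge fitness. The misclassification follows from the endpoint wording and the absence of a cancellation rule.
- **Both arms are pushed toward 100%, or failing ventricles go unseen.** If 40 of 50 reach the work-up, scored success cannot exceed 80%. Long-term secondary 6 measures right ventricular function at the work-up, the same visit includes an adverse event assessment, and Section 8.7 follows unresolved events until they resolve or stabilize. This cover is partial, because missing work-up data are tolerated.
- **Surgery performed would remove bias from knowing the arm.** The decision to operate is also made by clinicians who know the arm. The change deals with cancellations only.

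It is also fair to say that ending at a standard-of-care work-up is a deliberate low-burden choice. That explains the exit point, but not why it should apply to a child whose operation is then cancelled.

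**Conclusion.** The point holds, with a limited reach. Followed literally, the plan scores secondary 4 at scheduling, ends participation at the completed work-up, and has no rule for an operation cancelled afterwards. Such a child stays a success on secondary 4 and is lost to secondary 5.

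The size is unknown. The range of 0.8 to 4 children per arm rests wholly on the assumed 40 of 50 reaching work-up and the assumed 2% to 10% turn-down. The effect is confined to long-term secondary endpoints 4 and 5 and their place in the testing order. The primary endpoints and the sample size are untouched. It should still be settled before analysis: the change is cheap, and the children concerned are those in whom the outcome the product aims to prevent may have occurred.

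**What to change.** 1. Use one definition in the Summary, Section 2, Section 3.3 and Section 7.4.4, and align the Section 1 hypothesis with it. The preferred definition is Stage III surgery performed (yes/no, with date), taken from the medical record without an added visit. Report scheduling descriptively.
2. Add surgery performed and its date to the items in Section 6.3.4.
3. In the Summary, Section 2, Section 3.1.2, Section 6.3.3 and footnote 5 of Section 6.5, state that the work-up is not study exit when surgery is cancelled or deferred afterwards. The existing six-monthly phone and record follow-up then continues to 4 years, transplant or death, so that secondary 5 is complete.

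If the sponsor prefers to keep scheduling as the endpoint, the least it should do is reword the Summary methods and Section 7.4.4 to match, and state how later cancellations, listings and deaths are counted.

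The cost is one chart item, slightly longer record follow-up per child, continued phone contact for those whose surgery does not go ahead, and a small change to the participation-duration and consent wording, which needs IRB review. No test or clinic visit is added.
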